10.4.3. Statistical Methods

Clinical laboratory test will be summarized at each visit during the treatment period. The baseline value will be the last measurement on or before the day of the infusion of study drug. This same baseline value will be used for all changes from baseline tables in the treatment period and post-treatment period. Natural history control data is not available for this evaluation.

Mean changes from baseline to End of Study/Early Termination will be summarized for each protocol-specified laboratory parameter with the baseline mean, visit mean, change from baseline mean, standard deviation, minimum, maximum, and median.

During the treatment period, laboratory data values will be categorized as low, normal, or high based on normal ranges of the laboratory used in this study. Shift tables from baseline to minimum value, maximum value, and final values during the treatment period will be created. The shift tables will cross tabulate the frequency of patients with baseline values below/within/above the normal range versus minimum/maximum/final values below/within/above the normal range.

The number and percentage of patients with post-baseline values during the treatment period meeting the specified criteria for Potentially Clinically Significant (PCS) laboratory values will be summarized. A post-baseline value must be more extreme than the baseline value to be considered a PCS finding. A listing will be provided that presents all of the lab values for the patients meeting PCS criteria during treatment Period.

For hemoglobin and the liver function tests (LFTs) of ALT, AST, alkaline phosphatase, and total bilirubin, the number and percentage of patients in each treatment group with a maximum CTCAE Grade of 1, 2, 3, or 4 (as defined by the central laboratory and based on CTCAE v4.03) at any post-baseline visit (regardless of the baseline value) through the end of treatment (i.e., Final Treatment Value) will be summarized. All LFT tables will include summary rows for the number and percentage of patients with at least Grade 2 and at least Grade 3 laboratory abnormalities. The hemoglobin table will include a summary row for the number and percentage of patients with at least a Grade 2 laboratory abnormality. Listings of all ALT, AST, total, indirect and direct bilirubin, and alkaline phosphatase will be created for any patients who had at least a Grade 3 ALT, AST, alkaline phosphatase, or total bilirubin. A listing of hematology results will be provided for patients with hemoglobin abnormalities.

For patients with a Grade 3 or higher total bilirubin elevation, a listing of treatment-emergent adverse events (defined as preferred terms within the "Cholestasis and jaundice of hepatic origin" (broad search) SMQ, excluding preferred terms within the "Investigations" SOC) will be provided.

The number and percentage of patients meeting the following criteria will be summarized overall.

- ALT \geq 3x ULN with bilirubin < 2x ULN
- AST \geq 3x ULN with bilirubin < 2x ULN
- ALT \geq 5x ULN with bilirubin < 2x ULN
- AST \geq 5x ULN with bilirubin < 2x ULN
- ALT \geq 10x ULN with bilirubin < 2x ULN
- AST \geq 10x ULN with bilirubin < 2x ULN
- ALT \geq 20x ULN with bilirubin < 2x ULN
- AST \geq 20x ULN with bilirubin < 2x ULN
- ALT \geq 3x ULN with bilirubin \geq 2x ULN
- AST \geq 3x ULN with bilirubin \geq 2x ULN
- ALT \geq 5x ULN with bilirubin \geq 2x ULN
- AST \geq 5x ULN with bilirubin \geq 2x ULN
- ALT \geq 10x ULN with bilirubin \geq 2x ULN
- AST \geq 10x ULN with bilirubin \geq 2x ULN
- ALT and AST \geq 3x ULN with bilirubin < 2x ULN
- ALT and AST \geq 5x ULN with bilirubin < 2x ULN
- ALT and AST \geq 10x ULN with bilirubin < 2x ULN
- ALT and AST \geq 3x ULN with bilirubin \geq 2x ULN
- ALT and AST \geq 5x ULN with bilirubin \geq 2x ULN
- ALT and AST \geq 10x ULN with bilirubin \geq 2x ULN
- ALT and AST \geq 20x ULN with bilirubin \geq 2x ULN

A patient or event will be counted if the post-baseline laboratory values meet the above criteria regardless of the baseline laboratory value (i.e., the post-baseline laboratory value does not need to be worse than the baseline laboratory value). For patients meeting any elevation criterion, a corresponding listing of all ALT, AST, alkaline phosphatase, and total, direct, and indirect bilirubin values will be provided.

10.4.4. Drug-Induced Liver Injury

Drug-induced liver injury (DILI) has been the most frequent single cause of safety-related drug marketing withdrawals and as such with this pediatric population (SMA patients) and unique intervention (gene therapy), Sponsor took care to assess hepatic test results as drugs can cause liver injuries by many different mechanisms. Severe DILI cases rarely have been seen in drug development programs of significantly hepatotoxic drugs that do cause such injury. Evidence of hepatocellular injury is thus a necessary, but not sufficient, signal of the potential to cause severe DILI (note, however, that the drugs causing hepatic injury through mitochondrial toxicity may not cause early hepatotoxicity).

It is possible that although a drug may not cause severe liver injury, it could still result in laboratory evidence of mild, transient hepatic injury, with leakage of liver enzymes and the appearance in serum of elevations in aminotransferase activities to levels of 3, 5, and sometimes greater than 5 times the upper limits of normal (ULN). The liver enzyme data was evaluated according to these criteria and according to Hy's Law.

A finding of ALT elevation, usually substantial, seen concurrently with bilirubin >2 ULN, identifies a drug likely to cause severe DILI (fatal or requiring transplant) at a rate roughly 1/10 the rate of Hy's Law cases. It is critical to rule out other causes of injury (e.g., other drugs or viral hepatitis) and to rule out an obstructive basis for the elevated bilirubin, so that alkaline phosphatase (ALP) should not be substantially elevated. In all cases to date, the small number of Hy's Law cases has arisen on a background of an increased incidence of more modest signs of hepatocellular injury (e.g., greater incidence of 3xULN elevations in AT than seen in a control group).

Briefly, Hy's Law cases have the following three components:

- The drug causes hepatocellular injury, generally shown by a higher incidence of 3-fold or greater elevations above the ULN of ALT or AST than the (nonhepatotoxic) control drug or placebo.
- Among trial patients showing such AT elevations, often with ATs much greater than 3xULN, one or more also show elevation of serum TBL to >2 ULN, without initial findings of cholestasis (elevated serum ALP).
- No other reason can be found to explain the combination of increased AT and TBL, such as viral hepatitis A, B, or C; preexisting or acute liver disease; or another drug capable of causing the observed injury.

For patients enrolled in this study these criteria are assessed in order to determine both general liver function enzyme changes (LFEs) according to change from baseline and over course of study. In addition, the assessment of changes in ALT or AST relative to TBL allowed assessment if a signal related to DILI occurred in any individual or group of patients.

10.5. Vital Signs

Vital signs (pulse, respiration, temperature, diastolic blood pressure, body weight, systolic blood pressure, pulse oximetry) will be examined at each visit. Clinically-significant, treatment-emergent findings will be reported as adverse events.

A summary of changes from first recorded value in vital signs will be described at each visit on the safety set. In addition, vital signs results will be flagged as Potentially Clinically Significant (PCS) if they meet the pre-specified criteria. The number and percent of patients meeting each PCS criterion will be summarized starting at Day 1 and continuing through the end of study.

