Study Day	For any event of interest, Study Day = calendar date of event – calendar date of gene transfer +1. Day 1 is the Study Day of the gene transfer and any events occurring on the same calendar day as the gene transfer.
TEAE	Treatment-emergent Adverse Event = any adverse event whose onset (or worsening of an existing AE) occurred on or post day of gene therapy infusion.

Abbreviation	Description
Vector genome	The human SMN cDNA sequence, corresponding to the mature mRNA, cloned into the self-complementary AAV vector plasmid.

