b Day 1 assessments will be performed prior to the start of gene replacement therapy infusion.

c The 14 months of age visit must occur within 0 to 14 days after the date on which the patient reaches 14 months of age.

d Developmental milestones will be assessed as defined by Bayley Scale of Infant and Toddler Development, version 3 (independent sitting will be assessed also by WHO Multicentre Growth Reference Study).

e Videos may be submitted for review by a central reader.

f The full Bayley test will be administered every 6 months, starting at Month 6, whereas the Bayley fine and gross motor subtests will be administered at each monthly visit.

g Patients who achieve 3 consecutive CHOP-INTEND scores ≥ 58 will not continue CHOP-INTEND assessments.

h Vital signs include blood pressure, respiratory rate, pulse, axillary temperature, and pulse oximetry

i Vital signs will be continuously monitored throughout the infusion of gene replacement therapy and recorded every 15 minutes for the first 4 hours after the start of infusion, then every hour until 24 hours after the start of infusion. Axillary temperature will be recorded pre- and post-infusion.

j Completed every 6 months, starting at Month 6.

k Serial ECG data will be pulled in triplicate from the Holter monitor at the following time points: pre-dose (within 24h), 2h, 4h, 6h, 8h, 12h, 24h, 36h, and 48h post-dose.

l Additional sampling may be performed at subsequent time points if ELISpot value(s) continue to be elevated, based on further discussion with the Principal Investigator and Medical Monitor.

m Collected at 24 and 48 hours post-dose.

n Serious adverse events are collected from signing of the informed consent through the last study visit. All adverse events that occur from the start of gene replacement therapy through the last study visit are collected.

- o Laboratory samples collected on Day 1 to be processed locally, prior to dosing.
- p Sites participating in the viral shedding sub-study will collect 24-hour full volume samples for urine and feces at 24 and 48 hours. All other sites will collect singular urine and feces samples within 24 hours and 48 hours of dosing.
- q Prednisolone to be given 24 hours prior to scheduled AVXS-101 dosing, and continued as per protocol Section 9.2.1.
- r CK-MB will be collected at Day 60, Month 6, 9, 12, 15, and 18

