6.2. Key Definitions

6.2.1. Definition of Baseline

The baseline value refers to the last non-missing measurement collected before gene therapy infusion of study drug. On Study Day 1, all assessments should be performed prior to administering the gene therapy infusion of study drug per protocol. The baseline value is therefore determined by the last non-missing measurement collected on or before the first day of study drug administration. If multiple measurements are recorded on the same day, the last measurement recorded prior to the gene therapy infusion will be used as the baseline value. If these multiple measurements occur at the same time or time is not available, then the average of these measurements (for continuous data) or the worst among these measurements (for categorical data) will be considered as the baseline value. This same baseline value will be used for the treatment and post-treatment periods. For some special measures, the baseline value will be defined explicitly in the corresponding section.

The baseline values will be the first non-missing values collected for the control patients from the PNCR dataset.

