Due to the difficulty in clinical operation, some landmark visits criteria, like 14 or 18 months of age visits, may not be attained in the protocol defined visit windows. As long as a formal landmark visit cannot be scheduled and the next planned visit is made, for example age of 15 months visit, or survival status is confirmed, for example still survived after age of 18 months, data collected at the unscheduled visit may still be able to map to the landmark visit and included in the corresponding landmark analysis. And protocol deviation will be filed accordingly.

Safety data, such as laboratory results, vital signs, ECGs, and physical exams will be assessed by date and study day. For change from baseline analyses the value associated with the scheduled visit will be used. For summaries of shifts from baseline and potentially significant values all values will be considered for these analyses. Baseline for safety measures will be defined as the latest value before Day 1.

The efficacy data of this study will be compared to the data from the PNCR network. The analysis visit of PNCR will be based on the Visit Month defined in the PNCR dataset.

Table 5: Analysis Time Windows for Dataset from PNCR Network

Scheduled Visit	PNCR
Baseline	≤ Enrollment Date
Month 2	Visit Month 2
Month 4	Visit Month 4
Month 6	Visit Month 6
Month 9	Visit Month 9
Month 12	Visit Month 12
Month 18	Visit Month 18

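### The vital-sign PCS count in SAP 10.5 starts at Day 1 rather than at the start of infusion, so a pre-infusion reading can be counted as an on-study finding (minor)

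*SAP*

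**What the plan says.** Section 10.5 flags a vital-sign result as PCS when it meets pre-specified criteria, which the SAP does not reproduce. It then fixes the counting window: "The number and percent of patients meeting each PCS criterion will be summarized starting at Day 1 and continuing through the end of study". It sets no clock time and does not require a post-infusion or post-baseline value.

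The glossary (1.2) defines the start of that window as a calendar day: "Day 1 is the Study Day of the gene transfer and any events occurring on the same calendar day as the gene transfer". Section 6.4 places vital signs on the same clock: "Safety data, such as laboratory results, vital signs, ECGs, and physical exams will be assessed by date and study day". The same paragraph of 6.4 says that all values are considered when shifts from baseline and potentially significant values are summarized.

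On measurements taken on Day 1, footnote i to the Schedule of Assessments (3.5.1) says: "Axillary temperature will be recorded pre- and post-infusion". It also says that vital signs are "recorded every 15 minutes for the first 4 hours after the start of infusion, then every hour until 24 hours after the start of infusion". Footnote b says: "Day 1 assessments will be performed prior to the start of gene replacement therapy infusion". Section 6.2.1 says much the same: "On Study Day 1, all assessments should be performed prior to administering the gene therapy infusion of study drug per protocol".

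**The concern.** The trial has one arm and no concurrent control. A reader of the safety tables will take the percentage with a PCS vital sign during the study as a description of what happened after AVXS-101 was given. A fever or abnormal pulse recorded on the morning of the infusion, before dosing, is not that. If the table includes it, the table mixes pre-existing abnormality with possible treatment effect, and no control column would reveal the mixture. With at most 20 treated children, one misplaced child is visible in the percentage.

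**Working it through.** The SAP gives no figure for this count, so there is none to reproduce. The check sets its rules side by side.

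1. **Window.** Section 10.5 opens the count at Day 1. By the glossary, Day 1 is the full date of gene transfer. By 6.4, vital signs are handled by date and study day. A reading taken that morning before dosing therefore has Study Day 1, and a program selecting Study Day 1 onward keeps it.

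2. **Are pre-infusion readings planned on Day 1?** For axillary temperature, yes: footnote i says so and is attached to the Day 1 vital-signs cell. For the other signs the support is weaker. Their timed schedule in footnote i begins at the start of infusion, so a pre-infusion Day 1 reading rests only on the general sentences in footnote b and 6.2.1.

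3. **Does a baseline rule remove the reading?** The SAP gives three reference values:
   - Section 6.2.1: where several readings fall on the same day, "the last measurement recorded prior to the gene therapy infusion will be used as the baseline value". A pre-infusion Day 1 reading may then be the baseline.
   - Section 6.4: the safety baseline is the latest value before Day 1. A pre-infusion Day 1 reading is then later than baseline.
   - Section 10.5: vital-sign changes are measured from the first recorded value. With vital signs also scheduled at screening and on Day -1, that is normally an earlier reading.

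   The PCS count in 10.5 refers to none of these, so the reading stays in whichever rule applies.

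4. **Does another general rule remove it?** No. The all-values sentence in 6.4 points towards keeping it.

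5. **Comparison with the other PCS counts.**
   - Laboratory PCS (10.4.3): post-baseline values only, and more extreme than baseline.
   - Holter PCS (10.7): starts at the 2-hour time point, although a pre-dose time point exists.
   - Vital-sign PCS (10.5): starts at Day 1 with no such limit.

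6. **Size per child.** The inputs are up to 20 patients enrolled and at least 15 expected to meet ITT criteria (3.7). The safety population is everyone infused, so 20 is the largest denominator, and 15 is used as an assumed lower value.
   - Shift per affected child = 1/n.
   - n = 20: 1/20 = 5.0 percentage points.
   - n = 15: 1/15 = 6.7 percentage points.

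   The number of affected children depends on data and criteria that the SAP does not contain, so no total can be given.

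**The case against.** The best case on the other side has five parts.

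- **The all-values sentence in 6.4 is a stated convention, and 10.5 merely applies it from Day 1.** This stands in part: the inclusion follows from the text and is not a gap in it. It does not make a pre-treatment value an on-study finding, and the laboratory and Holter PCS counts do not follow it to that point.

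- **The contrast with other sections is not uniform.** Section 10.6 promises a listing of all PCS ECGs with no post-dose limit. This is correct. A dated listing lets the reader see when each value was taken, however, which a count of patients does not.

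- **A reader might infer that the baseline itself is counted.** The SAP does not support that without qualification. It follows under 6.2.1 but not under 6.4 or 10.5, where the reference value is earlier. The point here does not depend on which rule governs.

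- **A reader might infer a large effect from how few Day 1 temperature readings footnote i names.** The SAP does not support that either. The table counts patients, not readings, and its window runs to the end of study with vital signs at every visit. If the count is pooled over time, a child is miscounted only when the pre-infusion value is that child's sole PCS reading for the criterion. If it is by time point, only the Day 1 row is touched, and a separately labelled pre-dose row would remove the problem.

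- **The criteria and table shells are kept outside the SAP and might add the limit, and any error over-counts abnormality.** Both are fair. Section 10.5 itself sets the window, though, so the limit belongs there. Clinically significant treatment-emergent findings are reported as adverse events in any case, so this wording does not hide harm.

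**Conclusion.** The point holds as a minor one. As written, 10.5 lets a reading taken before the infusion on Day 1 count in the on-study vital-sign PCS table. This is clear for axillary temperature and rests on general wording for the other signs. Each child affected moves a criterion by 5.0 percentage points at n = 20, or 6.7 at n = 15. The number affected is unknown and may be zero. The conclusion assumes that the unseen PCS criteria and table shells do not already exclude pre-infusion values. No test, endpoint or decision rule depends on this table.

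A reader might also infer that unchanged abnormalities should be left out of the count. The SAP does not support that as a correction. It requires worsening for laboratory PCS but expressly does not for the liver-enzyme thresholds, both in 10.4.3, so either convention is open for vital signs.

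**What to change.** In 10.5, state that the count includes only values recorded after the start of infusion on Day 1 through the end of study. Show each child's PCS status before the infusion in a separate column, so that pre-existing abnormalities stay visible. A condition that the value be more extreme than baseline is optional.

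The cost is one sentence and one column, with no new data. Some counts, mainly for temperature, may become slightly smaller.

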10.6. ECG

Serial ECG data will be pulled in triplicate from a Holter monitor at the following time points and will be provided in an external dataset:

- Pre-dose (within 24 hours prior to gene replacement therapy)
- 2 hours
- 4 hours
- 6 hours
- 8 hours
- 12 hours
- 24 hours
- 36 hours
- 48 hours

A 12-lead ECG will be conducted at scheduled visits of Screening, Day 1, Day 2, and every 6 months through 18 months of age, and assessed by a central reviewer. The baseline value will be the average of all measures within 6 hours of prior to dosing. Mean changes from baseline, standard deviation, minimum, maximum, and median to End of Study/Early Termination visit will be summarized for HR, PR, QR, QRS, QTcF.

The central reviewer will identify abnormal ECGs that are PCS, the definitions for which are maintained outside of this document.

A listing of all PCS ECGs will be provided. Summaries of ECG data will be presented overall.

10.7. 12-Lead Holter Monitor

A Holter monitor will continuously record the patient's 12-lead ECG for a total of 72 hours from Day -1 (24 hours prior to the start of gene replacement therapy infusion) through 48 hours after the start of infusion. On Days -1 to Day 3, serial ECG data will be pulled in triplicate from the Holter monitor at time points of 'pre-dose', '2 hour', '4 hour', '6 hour', '8 hour', '12 hour', '24 hour', '36 hour' and '48 hour' post-dose and assessed by a central reviewer. The triplicate of each parameter for HR, PR, QRS, QTcF, as measured by the central reviewer, at each time point will be averaged for summaries. The summaries of Holter monitor data will be done by the actual treatment received overall.

Twenty-four-hour Holter monitoring will also be performed at the 3, 6, 9, and 12-month visits and every 6 months thereafter.

The central reviewer will identify abnormal ECGs that are PCS based on central reviewing guidelines provided by BMS. The number and percent of patients meeting each PCS criterion will be summarized starting at '2 hour' and continuing through '48 hour'.

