4.6.7. Cardiovascular Safety Evaluations

A 12-lead electrocardiograms will be conducted on the schedule of assessment (Table 1). The ECG tracings or ECG machine data will be collected for centralized review and interpretation by a cardiologist.

Additionally, a Holter monitor will be placed 24 hours prior to dose administration through 48 hours after dose administration. On Day -1 to Day 3, serial ECG data will be pulled in triplicate from the Holter monitor at the following time points:

- Pre-dose (within 24 hours prior to gene replacement therapy)
- 2 hours
- 4 hours
- 6 hours
- 8 hours
- 12 hours
- 24 hours
- 36 hours
- 48 hours

Twenty-four hour Holter monitoring will also be performed at the 3, 6, 9, and 12 month visits and every 6 months thereafter.

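### SAP 10.7 limits the Holter PCS count to 2–48 hours after dosing and so leaves out the planned follow-up Holters; separately, Table 1 disagrees with 4.6.7 and 10.7 about Holters at Months 3 and 9

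*SAP*

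**What the plan says.** **Holter count.** Section 10.7 describes a continuous in-patient Holter from 24 hours before to 48 hours after the start of infusion, with triplicate ECG extractions at fixed time points. It then adds: "Twenty-four-hour Holter monitoring will also be performed at the 3, 6, 9, and 12-month visits and every 6 months thereafter". On PCS findings it says: "The central reviewer will identify abnormal ECGs that are PCS based on central reviewing guidelines". The patient count follows at once: "each PCS criterion will be summarized starting at '2 hour' and continuing through '48 hour".

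**General rule.** Section 6.4 opens its safety paragraph with "Safety data, such as laboratory results, vital signs, ECGs, and physical exams will be assessed by date and study day". It then uses scheduled-visit values for change from baseline, and continues: "For summaries of shifts from baseline and potentially significant values all values will be considered for these analyses".

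**Neighbouring sections.** For 12-lead ECGs, Section 10.6 specifies "A listing of all PCS ECGs will be provided" but no number and percent of patients with PCS findings. Section 10.5 counts vital-sign PCS findings from Day 1 to the end of study.

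**Holter schedule.** Section 4.6.7 agrees with 10.7: "Twenty-four hour Holter monitoring will also be performed at the 3, 6, 9, and 12 month visits and every 6 months thereafter". In Table 1 (Section 3.5.1), the monthly entry in the Holter row carries footnotes j and t. Footnote j gives six-monthly assessments beginning at Month 6. Footnote t gives children enrolled before amendment 3 one Holter at their next visit and then returns them to the Table 1 schedule. Table 1 also has a Holter at End of Study.

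**The concern.** The follow-up Holters are planned, and the PCS sentence in 10.7 sets no time limit on the central reviewer's task. Yet the only PCS number and percent specified for ECG data stops two days after infusion. A child whose sole PCS finding is on the Month 6 Holter is left out of the 10.7 count. On one natural reading of 6.4 that child belongs in it. The SAP does not say how the two sections fit together, so two programmers could each follow the document and report different percentages.

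Safety is a stated objective (3.4), and cardiac events, arrhythmias among them, are of special interest (10.3.2.4). A 48-hour PCS percentage could be taken for the whole study's Holter result.

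The schedule discrepancy adds to this. Once follow-up recordings are counted, someone must know whether a child without a Month 3 or Month 9 Holter has missing data or was never due one. Under 10.6 ("A 12-lead ECG will be conducted at scheduled visits of Screening, Day 1, Day 2, and every 6 months through 18 months of age") and footnote j, no 12-lead ECG is routinely due at those months either, so the Holter would be the only routine ECG recording there.

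**Working it through.** The plan states no figure to reproduce. The check compares the texts and counts scheduled recordings.

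**1. What the 10.7 count covers.** The post-dose time points are 2, 4, 6, 8, 12, 24, 36 and 48 hours: 8 time points, and no follow-up visit.

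**2. Inputs for the follow-up count.**
- Age at dosing is below 180 days, so at most 179 (5.2).
- End of Study falls 0 to 14 days after 18 months of age, that is, at age 540 to 554 days (3.5, 6.2.3).
- Month 12 is Study Day 360, window 345 to 374. Month 18 is Study Day 540 (Table 4).
- Study Day = age at visit − age at dosing + 1 (from the definitions in 1.2).

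**3. Does every completing child reach Month 12?** The earliest End of Study is 540 − 179 + 1 = Study Day 362, which is after Study Day 360. So yes.

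**4. Can Month 12 and End of Study coincide?** End of Study can fall in the Month 12 window when 540 − dosing age + 1 ≤ 374, that is, at dosing ages 167 to 179 days. One recording may then serve both visits.

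**5. Does Month 18 add a recording?** Study Day 540 comes no later than age 554 only if dosing age ≤ 554 − 540 + 1 = 15 days. It then lies inside the End of Study window, so it adds none.

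**6. Follow-up Holters per completing child on the regular schedule.**

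| Schedule | Visits | Number | If Month 12 and End of Study share a recording |
|---|---|---|---|
| 4.6.7 and 10.7, plus End of Study | Months 3, 6, 9, 12, End of Study | 5 | 4 |
| Table 1, footnote j | Months 6, 12, End of Study | 3 | 2 |

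Difference: 5 − 3 = 4 − 2 = 2 per child (Months 3 and 9), so up to 2 × 20 = 40 recordings in 20 children. The 10.7 count uses none of the recordings in either row.

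**7. Effect of footnote t.** It can add one catch-up recording, for example at Month 2, giving 5 + 1 = 6 or 3 + 1 = 4. A child enrolled before amendment 3 may also lack earlier recordings. The SAP does not give the number of such children, so no trial total is derived. Footnote t does not add Months 3 and 9, because it refers back to Table 1.

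**8. Effect on the reported percentage.** One child with a late-only PCS finding moves it by 1/20 = 5.0 points if 20 children are treated, or 1/15 = 6.7 points if 15 are. This is only the reciprocal of the sample size. How often such a finding would occur cannot be derived from the SAP.

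**The case against.** The strongest reply is that 10.7 is a specific rule that fits its data. Its time labels belong to the in-patient extraction series, and no extraction time points are given for the 24-hour follow-up Holters. Counting the in-patient series alone is a reporting choice and does not contradict having planned later recordings. That stands. It also means that adding a follow-up count requires a rule on which reading is used.

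Second, the all-values sentence in 6.4 follows one about scheduled-visit values, so it may mainly mean that unscheduled values count too. It names ECGs, not Holters. A reader might infer that 10.7 flatly contradicts 6.4, but the text does not establish that. Still, 10.7 calls what the reviewer flags ECGs, and nothing in 6.4 suggests that planned visits should be dropped.

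Third, a reader might infer that late cardiac findings go unread or unreported. The SAP does not support this. The PCS sentence in 10.7 has no time limit, although central assessment is spelled out only for the Day −1 to Day 3 extractions. The 10.6 listing has no time limit either, and cardiac adverse events are summarised through the last visit. With at most 20 children, a reader could count cases from a listing. But a listing supplies no percentage and no number of children recorded at each visit.

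Fourth, the protocol governs when Holters are done and is not at hand. So the SAP alone cannot show which of its two schedules is right.

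**Conclusion.** The point holds as a gap in descriptive safety reporting, minor to moderate in weight. Read literally, 10.7 leaves every follow-up Holter out of the only PCS number and percent specified for ECG data: 4 to 5 recordings per completing child on one schedule, 2 to 3 on the other. That sits awkwardly with 6.4, without being a proven contradiction. No efficacy test is affected.

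The discrepancy between Table 1 footnote j and Sections 4.6.7 and 10.7 is a direct contradiction about Months 3 and 9, worth 2 recordings per child. Its analytic effect is small until follow-up Holters are tabulated.

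The recording counts assume that each child completes follow-up on the regular schedule. That the follow-up Holters are centrally reviewed for PCS findings is inferred from the unrestricted sentence in 10.7.

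**What to change.** - **Section 10.7.** Keep the 2–48 hour PCS count and state that it covers the serial extractions. Add the number and percent of children with any central-reviewer PCS finding on a follow-up Holter through End of Study, with the number of children recorded at each visit. State which reading or readings from each 24-hour Holter are used, and how this count relates to 6.4.
- **Table 1.** Confirm the Holter schedule in the protocol, then make the Holter row, 4.6.7 and 10.7 agree. If Months 3 and 9 are required, give the Holter row its own footnote; footnote j also serves other rows, including the 12-lead ECG, where it agrees with 10.6. If they are not required, correct 4.6.7 and 10.7 instead.

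The cost is one small descriptive table, one rule for selecting readings and one schedule correction. The central reviewer's existing PCS guidelines can be used, and the planned tests do not change.
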